	9.1	С	Confidentiality	41
	9.2	S	Source Documents	41
	9.3	D	Data Collection	41
	9.4	R	Record Retention	41
	9.5	S	Safety and Quality Monitoring and Record Availability	41
	9.6	Α	Adverse event (AE) Reporting	42
	9.	6.1	Study Reporting Period of Adverse Events	42
	9.	6.2	Study Reporting Period for Serious Adverse Events	42
	9.	6.3	Notification of Serious Adverse Events	43
	9.7	S	Study Termination	43
1().	PU	BLICATION OF RESEARCH FINDINGS	44
1'	1.	LIS	ST OF ABBREVIATIONS	44
12	2.	RE	FERENCES	45
1:	3.	APF	PENDICES	47

List of Figures

FIGURE 1.1.1.1-1: PULMONARY LPS-INDUCED INFLAMMATION IS INHIBITED BY GLS-1027	15
FIGURE 1.1.1.1-2: PULMONARY LPS-INDUCED INFLAMMATION IS INHIBITED BY GLS-1027	16
FIGURE 1.1.1.2-2: GLS-1027 LOWERS PM2.5 INDUCED LUNG INFLAMMATION AND AIRWAY	
RESISTANCE	18
FIGURE 1.1.1.3-1: SARS-COV CASE-FATALITY RELATIVE TO PROVINCIAL AIR POLLUTION	
INDEX	19
FIGURE 1.2-1: STRUCTURE OF GLS-1027	21
FIGURE 1.2-2: STRUCTURE OF MICROCRYSTALLINE CELLULOSE	22

List of Tables	
TABLE 5.2-1. GLS-1027 AND PLACEBO DRUG PRODUCT VIAL LABELS	27

CLINICAL PROTOCOL SYNOPSIS

Title of study: Safety, Tolerability, Efficacy and Dose Response of GLS-1027 in the Prevention of Severe Pneumonitis caused by SARS-CoV-2 Infection

Number of study participants: 132

Study Phase: II

Study Type: Randomized, double-blind, placebo-controlled

Research Hypothesis: GLS-1027 will be safe, well tolerated and reduce the incidence of treatment failure as characterized by 1) advancing to WHO COVID-19 Classification level ≥6 which includes the need for intubation with mechanical ventilation, initiation of extracorporeal mechanical oxygenation (ECMO), or death, in SARS-CoV-2 infected hospitalized patients, 2) need for institution of salvage therapy 72 hours after study entry with either an IL-6 monoclonal antibody or dexamethasone (≥6 mg/day), 3) withdrawing consent from the study, 4) becoming lost to follow-up, or 5) discontinuation of treatment for any reason other than decrease in renal function or pregnancy.

Primary study objectives and outcome variables:

- Incidence of serious adverse events relative to treatment group
- Incidence of treatment failure within 28 days from enrollment

Exploratory study objectives and outcome variables:

- Assess the number of days requiring ICU care relative to treatment group
- Assess the number of days of mechanical ventilation relative to treatment group

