- 3. Able and willing to comply with study procedures
- 4. Enrollment within 72 hrs of hospitalization with a diagnosis of PCR confirmed SARS-CoV-2
- 5. WHO COVID-19 classification level 3 or 4

Exclusion criteria for enrollment:

- 1. Pregnant or lactating
- 2. SpO2 less than 90% on room air or less than 95% if on supplemental oxygen
- 3. Calculated GFR < 60 (Cockcroft-Gault)

4. Meets hospital COVID-19 treatment algorithm for treatment with dexamethasone at a dose of 6 mg/day for a 10-day course. A single bolus dose of 6 mg of dexamethasone given in the

Emergency Department and continued at a dose of \leq 3.5 mg/day or less is allowed.

- 5. Meets treatment algorithm criteria for treatment with toclizumab or other anti-IL-6 agent
- 6. Treatment with an anti-IL-6 inhibitor, anti-IL-1 inhibitor, anti-TNF monoclonal antibody, or anti-JAK inhibitor (see Appendix A exclusionary period for specific drugs)
- 7. Participation in a COVID-19 clinical trial that includes prescription of a drug with anti-cytokine activity
- 8. Treatment within the past 60 days with a chemotherapeutic agent
- 9. Current treatment with systemic corticosteroids at a dose equivalent of 20 mg/day or greater of prednisone or prednisolone, 16 mg/day or greater of methylprednisolone, or 4 mg/day or greater of dexamethasone
- 10. Diagnosis of leukemia or lymphoma
- 11. WHO COVID-19 classification level of 5 or greater (use of high-flow oxygen, non-mechanical ventilation such as CPAP, mechanical ventilation)

GeneOne Life Science, Inc.

GLS27-005 Clinical Protocol

Table S2: Schedule of Eve	ents	pe	r Sti	udy	Da	y																							-	
Tests and Observations	1	2	3	4	5	6	7	8	9	10	11	12	13	14	15	16	17	18	19	20	21	22	23	24	25	26	27	28	29	56 ^m
Clinical Evaluations																														
Obtain written Informed Consent	Х																													1
Confirm Eligibility Criteria	Х																													
Demographics	Х																													
Medical History	Х																													
Concomitant Medications	Х	Х	Х	Х	Х	Х	Х	Х	Х	Х	Х	Х	Х	Х	Х	Х	Х	Х	Х	Х	Х	Х	Х	Х	Х	Х	Х	Х	Х	Х
Review Medical Record	Х	Х	Х	Х	Х	Х	Х	Х	Х	Х	Х	Х	Х	Х	Х	Х	Х	Х	Х	Х	Х	Х	Х	Х	Х	Х	Х	Х	Х	Х
WHO COVID-19 Classification (Appendix B)	Х	Х	Х	Х	Х	Х	Х	Х	Х	Х	Х	Х	Х	Х	Х	Х	Х	Х	Х	Х	Х	Х	Х	Х	Х	Х	Х	Х	Х	Х
Safety Evaluations																														
Record Adverse Events	Х	Х	Х	Х	Х	Х	Х	Х	Х	Х	Х	Х	Х	Х	Х	Х	Х	Х	Х	Х	Х	Х	Х	Х	Х	Х	Х	Х	Х	Х
Record Vital Signs ^a	Х	Х	Х	Х	Х	Х	Х	Х	Х	Х	Х	Х	Х	Х	Х	Х	Х	Х	Х	Х	Х	Х	Х	Х	Х	Х	Х	Х	Х	Х

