2. HYPOTHESIS AND STUDY OBJECTIVES

2.1 Hypothesis

GLS-1027 will be safe, well tolerated and, for those admitted to hospital with PCR confirmed SARS-CoV-2 infection at WHO COVID-19 classification level of 3 or 4, will reduce likelihood for progression to WHO COVID-19 classification level of 6 or greater (defined as severe pneumonitis characterized by the need for intubation with mechanical ventilation, initiation of ECMO, or death) or need for salvage treatment started 72 hours after study entry with either an IL-6 monoclonal antibody or dexamethasone at a dose of $\geq 6 \text{ mg/day}$.

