4.5 Treatment with dexamethasone post-enrollment

Treatment with dexamethasone at a dose of 6 mg/day for 10 days is currently considered as part of the standard of care for COVID-19 at many institutions, however, the specifics of treatment and whether such treatment is formally algorithm based varies between institutions. Moreover, it is recognized that dexamethasone treatment may be ordered as part of clinical care for some subjects after enrollment into the study.

Enrollment into the study is allowed for individuals who have not been treated with dexamethasone since hospital admission. Enrollment into the study is also allowed for those have received a single bolus dose of 6 mg of dexamethasone at presentation to the hospital with or without continuation of dexamethasone at a dose of 3.5 mg/day or less.

Enrolled subjects for whom dexamethasone is initiated within 72 hours of the time of 1st dose of study drug will be considered to have required dexamethasone at the time of presentation to hospital and will be treated the same as those who received a single bolus dose of 6 mg at presentation to the hospital. Unless dexamethasone is prescribed for 10 days at 6 mg, sSuch subjects will not be considered to have met the definition of the need for salvage therapy, and will not be considered as meeting a study endpoint for failure.

Enrolled subjects for whom dexamethasone is ordered at a dose of ≥ 6 mg per day and is initiated 72 hours or later after the 1st dose of study drug will be considered to have met the definition of need for salvage therapy and thus have met a study endpoint for failure. Initiation of treatment with dexamethasone at a dose of less than 6 mg/day after enrollment in the study will not be considered as treatment failure.

Subjects will be subgrouped for summary by concomitant bolus dexamethasone within 72 hours of enrollment versus no concomitant dexamethasone with 72 hours of enrollment.

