8.2 Sample Size

Based on the initial data obtained to date and data in the literature ^[1], it is anticipated that approximately 50% of subjects hospitalized with PCR-positive SARS-CoV-2 infections

(WHO COVID-19 Classification level 3 or 4) will progress to WHO COVID-19 classification level of 6 or greater as defined by one or more of the following: the need for intubation or mechanical ventilation (level 6), the need for ECMO (level 7), or any cause death (level 8). The sample size estimate for this proof of concept is based on Fisher's Exact two-sided test for 2 proportions using NQuery 8 (www.statsols.com). Estimates of admitted patients requiring salvage therapy is unknown, however, the clinical data set who require intubation is a likely subset of those whose condition worsens but do not progress to respiratory compromise.

Although the interim analysis will utilize masked treatment assignments, the O'Brien Fleming group sequential sample size estimation confirms that a single interim look would retain a cumulative exit probability of 70% with a cumulative alpha =0.05 after the final analysis using the target enrollment of 132 (44 per group) to detect a reduction of those reaching the endpoint of treatment failure, which includes advancing to WHO COVID-19 Classification level \geq 6 from 50% (SOC treated) to 25% in either treatment group of SOC plus GLS-1027. Other conditions also qualify a subject as treatment failure include: need for salvage therapy with IL-6 monoclonal antibody; or institution of salvage therapy with dexamethasone (\geq 6 mg/day), withdrawing consent from the study, becoming lost to follow-up, or discontinuation of treatment for any reason other than renal function or pregnancy. This study is not powered to assess statistically significant differences between GLS-1027 doses.

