8.3 Randomization

Randomization to treatments will occurred using a centralized randomization system. Randomization will be stratified by site to ensure equal distribution of treatments within each site. Subjects within each site will be randomly assigned in a 1:1:1 ratio to receive placebo, 120 mg GLS1027 or 360 mg GLS1027 daily for their duration of hospitalization or until intubation or mechanical ventilation constrains oral medication.

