8.6 Efficacy Analysis

The primary endpoint is treatment failure which is defined as any subject who achieved WHO level \ge 6 (intubation and mechanical ventilation, requirement for ECMO, or death) within 28 days of initiating treatment or who meet the following reasons for treatment failure:

- Receiving salvage therapy with either an IL-6 monoclonal antibody or for those who are prescribed daily dexamethasone starting 72 hours or later after the 1st dose of study drug within the 28-day primary treatment period.
- Lost to follow-up through hospital transfer, within the 28-day primary treatment period.
- Discontinuation of study drug for any cause prior to discharge will be considered as a treatment failure, except for those for whom study drug was suspended due to a decrease in renal function (creatinine clearance of < 60 mL/min), and those become pregnant during treatment. These subjects will be followed for the primary endpoint for up to 28 days post enrollment, and for up to 56 days for safety.

Subjects who complete 28 days of treatment but remain hospitalized without increase in WHO COVID-19 Classification level to ≥ 6 , will not considered be as treatment failures with respect to the primary endpoint.

The proportion of subjects in each treatment group who reach the study endpoint of treatment failure by 28 days will be compared to placebo using Fisher's Exact 2-sided test of proportions. Additionally, the frequency for each outcome (intubation, ECMO, death) will be determined within each group. The ITT, mITT and PP analysis populations will be used to analyze the primary endpoint.

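### Minor, protocol as supplied only: steroid salvage is defined by dexamethasone alone, so late rescue with an equivalent dose of another corticosteroid scores as success, and 8.6 omits the 6 mg/day threshold

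*Protocol*

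**What the plan says.** The protocol states the steroid part of treatment failure in several places.

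- Synopsis, research hypothesis: "need for institution of salvage therapy 72 hours after study entry with either an IL-6 monoclonal antibody or dexamethasone", at 6 mg/day or more. The synopsis failure list and 8.2 give the same drug and dose without a time.
- 2.1: "need for salvage treatment started 72 hours after study entry with either an IL-6 monoclonal antibody or dexamethasone at a dose of" 6 mg/day or more.
- 4.5: dexamethasone at 6 mg/day or more counts as failure under this clause: "initiated 72 hours or later after the 1st dose of study drug will be considered to have met the definition of need for salvage". By contrast, initiating "dexamethasone at a dose of less than 6 mg/day after enrollment in the study will not be considered as treatment failure". A start within 72 hours of the first dose is not salvage unless it is 6 mg for 10 days.
- 8.6, which defines the analysed endpoint: an IL-6 antibody, or failure "for those who are prescribed daily dexamethasone starting 72 hours or later" after the first dose. No dose is given.

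None of these mentions another corticosteroid or an equivalent dose, and protocol Appendix A lists no steroid. Equivalence appears only in the eligibility criteria. Synopsis exclusion 9 sets one cut-off at 20 mg/day prednisone or prednisolone, "16 mg/day or greater of methylprednisolone, or 4 mg/day or greater of dexamethasone". Body section 4.3 repeats the first two drugs, restricted to outpatient treatment, and gives no dexamethasone figure.

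The SAP cites protocol version 5.0 and a 14-day treatment period; the protocol as supplied has 28 days. SAP 8.1 defines salvage as a non-study immune modulator and names no steroid. SAP 8.3 makes corticosteroid use or non-use a subgroup.

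**The concern.** Salvage belongs in the composite because a patient who needs rescue immunosuppression has not been kept well by study drug. That reasoning does not depend on which corticosteroid the ward prescribes. Under the protocol's rules two patients with the same course and the same strength of rescue can receive opposite scores because of the drug name.

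Other steroids are foreseeable. Section 3 leaves standard of care to the hospital algorithm or local practice, and 4.5 says that dexamethasone practice varies between institutions. I found no protocol text that prohibits another steroid after enrollment or makes its use a failure.

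The missing dose in 8.6 is a second defect in the same rule. Anyone programming the endpoint from 8.6 would fail a late starter on 4 mg/day, whom 4.5 explicitly does not fail.

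**Working it through.** **1. How the rules score a case.** Take three patients, each starting a steroid on Day 6, more than 72 hours after the first dose. Each is discharged by Day 28 without relapse and meets no other failure criterion.

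| Late start | 4.5 | 8.6 |
|---|---|---|
| Dexamethasone 6 mg/day | failure | failure |
| Dexamethasone 4 mg/day | not a failure | failure |
| Methylprednisolone 60 mg/day | not covered | not covered |

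The third patient falls to the default. Discharge within 28 days without relapse is a success (4.4). Had the patient stayed in hospital past Day 28 without reaching WHO level 6, that would also be a success (8.6, 8.9).

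**2. Strength of the rescue.** The only ratio in the documents is synopsis exclusion 9, prednisone : methylprednisolone : dexamethasone = 20 : 16 : 4.

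- Dexamethasone 6 mg = 6 × 20/4 = 30 mg prednisone = 6 × 16/4 = 24 mg methylprednisolone.
- Methylprednisolone 60 mg = 60 × 4/16 = 15 mg dexamethasone.

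On that ratio the third patient receives 2.5 times the dose that makes the first a failure.

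**3. The plan's own figure.** Inputs from 8.2: 44 per arm, 50% against 25%, two-sided alpha 0.05, one O'Brien-Fleming look, stated power 70%. A two-look O'Brien-Fleming calculation at half and full information, by normal approximation with unpooled variance, gives 70.4%. The analysis test in 8.6 is Fisher's exact test. Its power, by summing binomial probabilities over all tables with p ≤ 0.05 and no interim look, is 61.1%. That gap is a separate matter; 61.1% is used below only as the baseline.

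**4. What missed failures would do.** The documents give no rate: "Estimates of admitted patients requiring salvage therapy is unknown" (8.2). Every loss below is an assumption.

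| Missed failures | Observed rates, placebo / active | Exact Fisher power |
|---|---|---|
| None | 50 / 25 | 61.1% |
| 5% of each arm's failures | 47.5 / 23.75 | 57.4% |
| 10% of each arm's failures | 45 / 22.5 | 53.4% |
| 2.5 points in each arm | 47.5 / 22.5 | 62.7% |
| 5 points in each arm | 45 / 20 | 64.2% |

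A loss proportional to each arm's failures shrinks the difference and costs power. An equal absolute loss keeps the 25-point difference, moves both rates away from 50% and adds a little. The direction is not fixed.

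**5. Single results.** One patient is 1/44 = 2.3 points. Two-sided Fisher p-values with 44 per arm:

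- 22 v 11 (the planned rates): 0.027
- 21 v 10: 0.025
- 20 v 9: 0.023
- 20 v 10: 0.042
- 20 v 11 (two missed in placebo, none in active): 0.073

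The last case is a chance imbalance, not an expected one, but it shows how few patients matter at this size.

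**6. Type I error.** With equal true rates the exact size is 2.6% at 50/50 and 2.7% at 45/45, both below 5%.

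**The case against.** The strongest objection is that the SAP does not carry this component. It follows protocol version 5.0, replaces dexamethasone and IL-6 salvage with a non-study immune modulator, and treats corticosteroids as a class in a subgroup analysis. This stands: under the SAP endpoint the contrast between steroids does not arise. SAP 8.1 also counts high-flow oxygen or non-invasive ventilation, so some of these patients would fail there anyway. The point is confined to the protocol as supplied.

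Second, nothing shows that another steroid was used for rescue. Section 4.5 describes dexamethasone 6 mg/day for 10 days as standard of care at many institutions, so naming it is a defensible choice. This also stands, and it keeps the point minor. It does not make the rule scoreable when another steroid is given, and it does not reconcile 8.6 with 4.5.

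Third, an eligibility cut-off is not a conversion rule, and 4.3 does not repeat it for dexamethasone. This is correct: 30 mg and 24 mg are what the synopsis implies, not doses that the protocol endorses for the endpoint.

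A reader might infer that the gap favours one arm or inflates false positives. The documents do not support that. The trial is double-blind and "Randomization will be stratified by site to ensure equal distribution of treatments within each site", so local prescribing habits should be balanced across arms.

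**Conclusion.** The point holds for the protocol as supplied and is minor. Steroid salvage depends on the drug name, and the dose threshold is missing from the section that defines the analysed endpoint. Both can mis-score individual patients on a primary outcome.

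The size cannot be estimated from the documents. The frequency may be zero, and the power range of 53.4% to 64.2% rests wholly on assumed losses. Misclassification is expected to be non-differential, with no inflation of type I error and no fixed direction for power. It would be wrong to conclude that the SAP's planned analysis is affected or that the trial's comparison is biased.

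**What to change.** In 4.5 and 8.6 define steroid salvage as *dexamethasone ≥6 mg/day or an equivalent daily dose of another systemic corticosteroid, started 72 h or later after the first dose of study drug*. Align the synopsis, 2.1 and 8.2. This also restores the dose in 8.6.

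Three things should be stated with it.

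- The synopsis hypothesis and 2.1 count 72 hours from study entry; 4.5 and 8.6 count from the first dose. Say openly that the change adopts the first-dose anchor. The two can differ, because 1.3 allows dosing to begin the day after enrollment.
- Apply the 4.5 exception for starts within 72 hours (6 mg for 10 days) to equivalent doses in the same way.
- Prespecify a conversion table. The synopsis ratio implies 30 mg prednisone or prednisolone and 24 mg methylprednisolone. The sponsor should confirm these and add hydrocortisone.

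If the SAP endpoint is the intended one, no steroid rule is needed. SAP 8.1 should then say that corticosteroids are outside salvage and that Appendix A means the protocol's agent list, since the SAP's own Appendix A holds programming specifications.

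The cost is wording plus one dose-conversion derivation. SAP Listing 16.2.4.3 already shows start date, study day, dose, units, route and frequency. It shows no start time, so the 72-hour cut needs times to be collected or a stated day-based rule. Two further downsides are a slightly higher failure rate in all arms, and the counting of steroids given for other indications, as already happens with dexamethasone.

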2.2 Primary Objectives and Outcome Variables

- Incidence of serious adverse events relative to treatment group
- Incidence of treatment failure within 28 days from enrollment

2.3 Exploratory Objectives

- Assess the number of days requiring ICU care relative to treatment group
- Assess the number of days of mechanical ventilation relative to treatment group
- Assess incidence of WHO COVID-19 Classification levels relative to baseline serum IL-6 level
- Assess incidence of WHO COVID-19 Classification levels relative to baseline serum ferritin level
- Assess incidence of WHO COVID-19 Classification levels relative to baseline CRP
- Assess trough level of GLS-1027 relative to serum creatinine
- Assess the maximal level of Positive End-Expiratory Pressure (PEEP) for subjects who are intubated relative to treatment group.
- Assess the number of days of PEEP > 5 cm H₂O for subjects who are intubated relative to treatment group
- Incidence of progression to WHO COVID-19 Classification level 6, or 7, or 8 (individually)
- Assess SARS-CoV-2 IgM antibody responses relative to treatment group

3. STUDY DESIGN

This is a Phase II, randomized, double-blind, placebo-controlled study to assess 2 dose levels of GLS-1027 for the prevention of treatment failure among participants admitted to hospital with PCR confirmed infection with SARS-CoV-2 (WHO classification 3 or 4). The enrollment period will extend to 72 hours from hospital admission.

Participants will be randomized to placebo or GLS-1027 at either 120 mg or 360 mg daily in a 1:1:1 ratio as adjunctive to standard of care based on the hospital COVID-19 treatment algorithm and/or local COVID-19 treatment practices. Participants will be administered study drug for a maximum treatment period of 28 days or until discharge or death, whichever comes first. Follow-up will continue through to Day 56 to document AEs and outcome as to discharge, death, or WHO COVID-19 classification level if subject remains hospitalized.

3.1 Safety Monitoring

Participants will be monitored by hospital personnel as per protocol. Clinical adverse events (AEs) will be reviewed daily through to discharge or the end of the treatment period. Safety monitoring will also include laboratory assessment of hematology, chemistry and ECG as per the Schedule of Events. Serum trough levels of GLS-1027 will be assessed at select times throughout the trial as per the Schedule of Events. Participants will also be followed for up to 56 days post-enrollments for health status and adverse events.

3.2 Data and Safety Monitoring Board (DSMB)

In addition to internal monitoring of safety data by the site PI and medical monitor, an independent data and safety monitoring board (DSMB), consisting of expert members not related to the clinical trial or sponsor staff will provide safety oversight. The DSMB will include at a minimum three members: a physician specializing in either Infectious Disease or Pulmonary / Critical Care, a second health-care practitioner who may be a physician, and someone with statistical experience (physician or non-physician).

The DSMB will meet at the start of the clinical trial to review and finalize the DSMB charter. At a minimum, the DSMB will meet to review interim data when 50% of the target enrollees (66 subjects) have completed the primary observation period to discharge, death, discontinuation or 28 days of treatment. The DSMB will review safety data and outcomes for enrolled subjects in a blinded manner. Unless a safety signal has been encountered, enrollment will continue through to at least 44 per group (total N=132).

A summary of all AEs and SAEs will be provided to the DSMB as masked treatment groups by an independent statistician together with a summary rates of retention in the study, and other relevant events. Reports will include a summary of participants' baseline characteristics, early study discontinuations, and a summary of participants who reach primary endpoint and/or end of study follow-up. The DSMB may recommend corrective measures, up to termination of the study for safety concerns. Study termination can be implemented by the Project PI, FDA, Sponsor, or site-specific or other supervising IRBs. Conference call or video conference meetings are allowed as necessary.

Additional details can be found in the DSMB Charter.

